## **Project Summary**

This Down syndrome (DS) speech intelligibility diagnostic treatment study (DS-DxTx) is a clinical intervention study assessing the efficacy of a novel speech treatment approach for individuals with DS. DS is a common genetic disorder that causes lifelong intellectual disability where speech intelligibility is typically compromised affecting quality of life. The clinical management of communication disorders in individuals with DS is a priority for NIH's National Institute on Deafness and Other Communicative Disorder (NIDCD). The proposed treatment addresses the void in speech intervention and is based on the Vocal Tract Development Laboratory's (VTLab) research findings on anatomic, acoustic and perceptual studies from speakers with DS. Having identified specific difficulties in the production and perception of select vowels, this treatment focuses on accurate vowel production, while combining and adapting two established speech treatment approaches on articulatory accuracy and motor learning. Findings from this clinical intervention study are expected to pave the path towards optimal management of speech intelligibility in speakers with DS. Findings are also expected to provide the preliminary data needed to bridge the gap towards an exploratory clinical research proposal on functional anatomy as an intervention strategy.

# Background and Significance

Down syndrome (DS) is a common genetic disorder that affects 1:691 live births each year in the United States. It usually results from three copies of chromosome 21 (trisomy 21) and causes lifelong intellectual disability where the average lifespan has doubled from 30 to 60 years. Speech intelligibility, an important indicator of communicative effectiveness, is typically compromised in DS. The ability to communicate is central to social interactions, and educational and vocational pursuits. Reduced speech intelligibility can severely limit the affected person's ability to enjoy full participation in these interactions and adversely affect quality of life. Few communication interventions are tailored to meet the needs of the Down syndrome behavior phenotype (Neil & Jones, 2018). However, to date, there is no evidence-based treatment guidance for DS (e.g., none listed in the Practice Portal of the American Speech-Language-Hearing Association) even though enhancing speech intelligibility, as a means to improve communication, is a high priority treatment goal that parents and others seek for individuals with DS. The goal of improved intelligibility through the lifespan is made all the more important given that the average lifespan for persons with DS has increased remarkably owing to improve health care. In fact, the 'clinical management of communication disorders throughout the lifespan in individuals with Down syndrome' is at the forefront of NIH-NIDCD's priorities.

The proposed DS diagnostic treatment study (DS-DxTx) addresses this void in speech intervention and is based on the culmination of research findings from the Vocal Tract Development Laboratory (VTLab) using anatomic, acoustic and perceptual studies in individuals with DS (with major findings summarized in the following paragraph). As noted above, currently there are no evidence-based speech treatment guidance for DS. The VTLab is in a unique position to address this deficit given research findings on the anatomic growth of craniofacial morphology in typically developing and atypically developing individuals (e.g. DS). Such comparisons permit understanding the role of typical and atypical functions (breathing, deglutition and speech) in shaping the anatomic structures in typically and atypically developing individuals during the course of development and across the lifespan (i.e. functional anatomy). In addition, the VTLab has examined the biological basis of speech development by examining anatomic-acoustic correlates using necessary equipment and established protocols to record and analyze typical and disordered speech. The VTLab has also examined the acoustic-perceptual correlates of speech intelligibility in DS (NIH-NIDCD grants R01DC-006282 and DS-Administrative supplement). Given the research-backed knowledge that guides this clinical treatment study, we expect that the findings will help pave the path towards the ultimate clinical management strategies to improve speech intelligibility in individuals with DS.

As described below, this speech intelligibility diagnostic treatment study (DS-DxTx) is a clinical intervention study assessing the efficacy of a novel speech treatment approach using a combination of two established speech treatment approaches (on articulatory accuracy and motor control) while adapting them to produce low vowels when feasible. While both vowel and consonant errors contribute to reduced speech intelligibility (Bunton et al., 2007; Van Borsel, 1996; van Bysterveldt et al., 2010; Wild et al., 2018), commonly used tests of articulation generally do not provide for comprehensive assessment of vowel production (Eisenberg & Hitchcock, 2010), and subsequently most speech-language pathologists focus on consonant articulation errors (phonology) and do not directly address vowels in treatment. One of the important finding from the VTLab's speech perception/intelligibility research in DS (Wild et al., 2018) was that the low vowels  $\alpha$  as in hot and  $\alpha$  as in hat had a higher frequency of perceptual errors than the high vowels /i/ as in heat and /u/ as in hoot, particularly in males. Furthermore, another VTLab finding using acoustic analysis of all vowels with perceptual speech intelligibility ratings revealed that word-intelligibility improved when the production of the low vowels /a/ and /æ/ had more distinctive second formants/vocal tract resonances (Vorperian et al., 2023 & 2019). Since these extreme vowels define the articulatory working space (i.e. space within the oralpharyngeal cavity for the tongue to produce/articulate all the speech sounds), it was hypothesized that the smaller anterior facial skeleton in speakers with DS limited/compressed the tongue's front/back movements to distinctly produce the vowels  $/\alpha$ /versus  $/\alpha$ /. Indeed, VTLab findings using anatomic measurements from medical imaging studies confirmed the smaller maxillary and mandibular measurements in DS (working manuscript). However, prior to entertaining a hypothesis that attribute the difficulty in low-vowel production to anatomic dysmorphologies, it was necessary to assess whether intensive treatment may play an important role in improving speech intelligibility. The proposed intervention is individualized and prioritizes the low vowels, yet also accounts for the multiple deficits (such as motoric, phonologic and hearing loss deficits) commonly present in individuals with DS. Therefore, as detailed below, the purpose of this study was to determine whether a treatment approach that focuses on the production of the low vowels, while combining and adapting two established treatment approaches on articulatory accuracy and motor learning, would improve speech intelligibility and more specifically the accuracy of vowel production in speakers with DS.

Findings are expected to pave the path towards optimal management of speech intelligibility in speakers with DS. Furthermore, the preliminary data from this clinical intervention study is expected to help bridge the gap towards advancing exploratory clinical trials addressing the role of upper airway functions on the developing anatomy in the oral and pharyngeal regions (functional anatomy).

### Specific Aims/Study Objectives

The proposed project is an intervention study aimed at determining the efficacy of a novel diagnostic treatment plan addressing speech intelligibility in individuals with Down syndrome (DS) as a means to improve communication and subsequently quality of life. Speech intelligibility is often compromised in children and adults with DS and a lifelong problem for many individuals (Fawcett & Paralego, 2009; Kent

& Vorperian, 2013; Kumin, 1994). Therefore enhancing speech intelligibility is a high priority treatment goal that parents and others seek for individuals with DS. The speech impairment underlying the reduced intelligibility, however, is particularly challenging to assess and treat because it is potentially associated with multiple factors, including, but not limited to, craniofacial and laryngeal dysmorphologies (e.g. shorted midface skeleton; laryngomalacia), motor impairments (hypotonia, dysarthria, and apraxia), phonological delay or disorder, dysfluency, and hearing loss (Kent & Vorperian, 2013). Individually and in various combinations, these factors affect nearly every aspect of speech production to interfere with intelligibility (Kent et al., 2021).

The proposed intervention study to implement on individuals with DS, as described in the following section, is based on the natural evolution of research in the Vocal Tract Development Laboratory (VTLab) – as summarized in the previous section –. It is rooted in VTLab research findings from anatomic (working manuscript), acoustic (Vorperian et al., 2022 & 2019; Vorperian and Kent, 2014; Kent and Vorperian, 2013) and perceptual studies (Kent et al., 2021; Wild et al., 2018) on individuals with DS that the VTLab has been studying since 2000 with funding support from NIH-NIDCD. This proposed diagnostic treatment study (DS-DxTx) utilizes a holistic intervention approach that accounts for the likely motoric, phonologic and hearing loss deficits in individuals with DS. The smaller midfacial skeleton in individuals with DS has been hypothesized to cause crowding in the oral and pharyngeal cavities resulting in the disruption of all functions performed in the mouth and throat specifically respiration, deglutition and speech. Thus, a number of drastic surgical/medical interventions, such as tongue reduction, mandibular extraction and palatal expansion are commonly performed by medical professionals to address obstructive sleep apnea and drooling. This study is expected to provide the data needed to assess treatment efficacy in improving speech intelligibility; also, to provide the preliminary data needed to clarify the extent to which craniofacial dysmorphologies affects reduced speech intelligibility. The preliminary data from this study is expected to inform future clinical trials that examine the role of oro-pharyngeal functions, as an intervention strategy during early childhood, in the development of the anterior facial skeleton (functional anatomy).

**Aim 1:** Determine the efficacy of a newly devised intensive speech diagnostic treatment plan (DS-DxTx) that combines two established treatment approaches on articulatory accuracy and motor control (Cycles and the Script programs that are documented to be efficacious with other speech disorders) while predominantly using the low vowels as described below in the Methods section.

Speech intelligibility is hypothesized to improve as phonological errors decrease. Perceptual measures to assess treatment efficacy include: **(a)** the HAPP-3 score of Total Occurrence of Major Phonological Deviations (TOMPD score = Word/Syllable Structure Omission Sum (that includes omission and consonant clusters) + Consonant Category Deficiencies Sum); and **(b)** Percent Words & Multisyllabic words Correct (with tabulation of percent consonants correct and percent vowels correct).

**Aim 2**: Determine the extent to which craniofacial dysmorphology affects reduced speech intelligibility using a combination of perceptual and acoustic measures.

Accuracy in the perceptual identification of the low vowels (percent vowels correct) is hypothesized to remain unchanged if reduced accuracy is predominantly due to craniofacial dysmorphologies (underdeveloped/shorted midface skeleton). Perceptual measure will include percent accurate identification of the low vowels /a/ versus /æ/ (% vowels correct) pre- versus post-treatment. Acoustic measure will include the first two resonant/formant frequencies of the vocal tract (F1 & F2) with

comparisons of pre- versus post- treatment acoustic measures (as well as VTLab TD normative values and DS acoustic data). Increased difference of the second resonant frequency (F2) for the low vowels / $\alpha$ / versus / $\alpha$ /, related to the functional front/back movement of the tongue in the horizontal plane, combined with improved perceptual identification of the low vowels (percent vowels correct) will implicate the effectiveness of intensive treatment on low vowels using articulatory accuracy and motor control.

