Each DS-DxTx session will include 40 minutes of the adapted Cycles program focusing on articulatory (phonological) training at the syllable/word level and 20 minutes of the adapted Script program for motor training at the sentence level. The adaptations are to ensure vowel-focused intervention to facilitate low vowel production stability with repeated practice. The Cycles phonological program is a treatment guidance for typically developing individuals with moderate to severe unintelligible speech (Hodson, 1992; Hodson, 2006; Hodson, 2011). The focus is on assessing and treating speech sound disorders in targeted patterns based on developmental phonology. The name 'Cycles' refers to periods where all phonological error patterns are facilitated in succession per target

phoneme (Hodson & Paden, 1991) with gradual increase in complexity per cycle. The program uses auditory bombardment (wearing personal amplification while hearing the target sounds), production drill and sound practice (i.e. repeating sounds, syllables, & words as practice) in facilitated context to yield accurate productions. The development phonological treatment is syllable units, consonant vowel (CV), VC, CVC or VCV, /s/ clusters and alveolars in words, then phrases. Currently, no efficacy data has been reported using the Cycles phonological treatment program with individuals with DS. However, individuals with DS often have moderate to severely unintelligible speech and a potential fluctuating history of otitis media (Hodson & Paden 1991). The Cycles design uses amplification and habituates accurate syllables through repeated practice which may assist with a fluctuating hearing loss and motor control planning (e.g., apraxia, dysarthria). Modifications to Cycles specific to this treatment plan is the vowel-focused intervention that establishes distinct contrasts of the low vowels  $/\alpha$  and  $/\alpha$  that may result from anatomic and/or motor limitations. Facilitating low vowel stability while still following the targeted cycles of phonological intervention repeated practice adheres to the Cycles program design. Reducing the variability and automatizing productions of anticipatory sounds at the syllable level may improve co-articulatory effects of consonant accuracy in words. Priority of  $/\alpha$  and  $/\alpha$  vowels will supersede other vowel productions within each cycle of the treatment program.

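### Aim 2 sets out to determine how far craniofacial dysmorphology reduces intelligibility, but no craniofacial dimension is measured and an unchanged result cannot establish an anatomical cause

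*Combined protocol and SAP*

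**What the plan says.** Under Specific Aims/Study Objectives, Aim 2 is to "Determine the extent to which craniofacial dysmorphology affects reduced speech intelligibility using a combination of perceptual and acoustic measures". The only prediction that mentions anatomy is that low-vowel accuracy "is hypothesized to remain unchanged if reduced accuracy is predominantly due to craniofacial dysmorphologies".

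The measures are perceptual identification of the two low vowels before and after treatment, and F1 and F2, with "comparisons of pre- versus post- treatment acoustic measures (as well as VTLab TD normative values and DS acoustic data" among the planned comparisons. The F2 difference between the two vowels is described as "related to the functional front/back movement of the tongue in the horizontal plane". A larger F2 difference "combined with improved perceptual identification of the low vowels (percent vowels correct) will implicate the effectiveness of intensive treatment".

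The same section lists other contributors to poor intelligibility: "motor impairments (hypotonia, dysarthria, and apraxia), phonological delay or disorder, dysfluency, and hearing loss". The Approach section says of the low-vowel contrasts that the difficulty is one "that may result from anatomic and/or motor limitations".

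Elsewhere in Specific Aims the purpose is put more modestly: "to provide the preliminary data needed to clarify the extent to which craniofacial dysmorphologies affects reduced speech intelligibility".

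**The concern.** To estimate the extent of an effect, a study must either measure the supposed cause or have a contrast that isolates it. Aim 2 appears to have neither. Its only route to anatomy is treatment response, and the prediction runs one way: if anatomy dominates, accuracy should not change. The reverse does not follow, since lack of change has several other explanations that the protocol itself names.

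At stake is what can be concluded from one of the study's two aims. The protocol expects the data to clarify the craniofacial contribution and to inform later trials. If the meaning of an unchanged or imprecise result is not fixed beforehand, such a result could be taken as support for an anatomical cause that this design cannot test.

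**Working it through.** The documents give no power, error rate, effect size or margin for Aim 2, so there is no figure of the plan's own to reproduce. The main check sets the sections side by side.

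**Step 1. Is anatomy measured?**
- *Participants: Identification and recruitment*: a cursory orthodontia history by phone. No dimension.
- *Measures: Baseline, Primary and Secondary Outcome Measures*: recordings, language sample, HAPP-3, PPVT, oral-motor exam, ICS, parent questionnaire and hearing screening at baseline. All but the PPVT are listed again after treatment. No imaging, cephalometry or facial measurement.
- *Statistical Considerations*: speech-language, acoustic and perceptual measures. No anatomical class of measure, and no analysis linking anatomy to intelligibility.
- *Background and Significance*: smaller jaw measurements are reported, but from the laboratory's earlier imaging work.

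The count of craniofacial dimensions planned in these boys is zero.

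**Step 2. Do the outcomes isolate anatomy?** Background and Significance gives a reason to look at F2: a smaller anterior facial skeleton is hypothesised to restrict front/back tongue movement. But F2 contrast then reflects tongue movement, which motor impairment also affects, and the Approach section allows for either origin. Comparison with typically developing norms and with other DS data shows how a boy's formants differ, not why.

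**Step 3. What can each result mean?**

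| Result after treatment | What it supports | What it leaves open |
|---|---|---|
| Low-vowel accuracy and F2 contrast both improve | Evidence against a fixed anatomical limit | How much of the remaining deficit is anatomical |
| F2 contrast improves, accuracy does not | Does not meet the joint criterion for treatment effectiveness | The cause of the remaining perceptual deficit |
| Unchanged | Compatible with an anatomical limit | Residual motor, phonological or hearing deficit; insufficient treatment |
| Imprecise | Nothing firm | All of the above, and a real gain that was missed |

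No row yields an extent of craniofacial effect.

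**Step 4. Illustration of the imprecision route.** The three baseline assessments and the comparison of each boy with himself come from Statistical Considerations. Everything else is assumed: baseline accuracy 60%, a true gain of 15 points, independent tokens, n low-vowel tokens per recording, and a pooled two-proportion z-test at two-sided 5% within one boy. The plan names no such test.

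With p₁ and p₂ the observed proportions before and after treatment, and p the pooled proportion:

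z = (p₂ − p₁) / √[p(1 − p)(1/n₁ + 1/n₂)], where n₁ = 3n, and n₂ = n (one post recording) or 3n (three pooled).

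For n = 20 and one post recording, n₁ = 60 and n₂ = 20. The pooled proportion is (36 + 15)/80 = 0.6375. The standard error is √[0.6375 × 0.3625 × (1/60 + 1/20)] = 0.124. An observed gain of about 1.96 × 0.124 = 0.24 is then needed for significance, well above the true 0.15.

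Exact binomial enumeration gives the probability that the true 15-point gain is non-significant:

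| Tokens per recording | One post recording | Three pooled |
|---|---|---|
| 10 | 0.88 | 0.77 |
| 20 | 0.78 | 0.57 |
| 40 | 0.60 | 0.30 |

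For baselines from 40% to 70% the ranges are 0.86–0.88, 0.77–0.80 and 0.54–0.62 with one post recording, and 0.72–0.78, 0.49–0.61 and 0.20–0.37 with three. Correlation between tokens within a session would reduce precision further. These figures show only that a non-significant test is weak evidence of no change in a single boy. They do not measure the defect in Steps 1 to 3, which would remain with unlimited tokens.

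**Step 5. Would measuring anatomy rescue the aim?** Suppose one dimension were correlated with change across the ten boys. The Fisher z half-width is 1.96/√(10 − 3) = 0.741. For an assumed correlation of 0.5 the 95% interval is −0.19 to 0.86; for zero it is −0.63 to 0.63. That could support an exploratory aim, not a useful estimate of extent.

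**The case against.** The strongest defence is that this is a diagnostic treatment. Specific Aims and Background and Significance say that the intervention allows for motor, phonological and hearing deficits. The Cycles component addresses phonology and uses amplification; the Script component addresses motor planning; severe hearing loss that would limit participation is excluded. If the other causes are treated and a deficit remains, anatomy becomes more plausible. F2 was also chosen deliberately as an indirect indicator, and the data are called preliminary.

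Much of this stands. It explains the design, makes improvement informative, and shows that the authors do not treat the study as definitive. It does not close the gap. Being addressed by treatment is not the same as being removed by it. Boys who fail the hearing screen may stay in the study, and no planned analysis uses hearing or oral-motor status to separate the causes. The formal aim still promises to determine an extent.

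Two stronger readings are tempting. A reader might infer that the study will attribute a null result to anatomy; the plan nowhere says so. A reader might also infer that an F2 gain without a perceptual gain has been left with no reading at all; in fact it fails the stated joint criterion for treatment effectiveness. What is missing is only what such a result says about anatomy.

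**Conclusion.** The point holds. As worded, Aim 2 cannot be answered: the extent of a craniofacial effect is not estimable from these measures, and the most the design can provide on anatomy is evidence against a fixed limit when both measures improve. This rests on the listed assessments and on the protocol's own account of rival causes, not on the illustrative probabilities, whose token count, baseline, gain, test and independence are all assumed.

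It should be fixed, but it is a defect of wording and interpretation in one of two aims. A reader might infer that Aim 2 is worthless or that the trial is undermined. The documents do not support that: the pre/post changes are worth estimating, and Aim 1, treatment and data collection are unaffected.

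**What to change.** Amend Aim 2 and Statistical Considerations, before outcome data are reviewed, as follows.

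1. Reword Aim 2 as estimating, for each boy, the change after treatment in low-vowel accuracy and in the F2 contrast between the two low vowels, each with a measure of uncertainty. State that the extent of a craniofacial effect is not estimated and that comparisons with typically developing and DS acoustic data are descriptive.
2. State that improvement on both measures, the joint criterion already in Aim 2, is evidence against a fixed anatomical limit and not proof that anatomy plays no part. State that an unchanged, imprecise or F2-only result will not be attributed to craniofacial anatomy and is hypothesis-generating, and that a non-significant test alone will not be read as unchanged.
3. Report each boy's hearing screening, oral-motor and HAPP-3 results, which are already collected, beside his Aim 2 result.

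The cost is a more modest Aim 2 conclusion. No new data are needed, and Aim 1 and treatment do not change.

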### Statistical Considerations

Analysis will entail using a multiple single-subject design (Byiers, 2012) where assessment of progress for each of the 10 male participants will be compared against himself. This is based on the expected variability in speech production across participants. Assessment measures will include: a) speech-language quantitative measures described below including phonetic transcription by a trained speech-language pathologist; b) acoustic measures; and c) perceptual measures for intelligibility score (percent correct) that the VTLab has been using and described in detail in Wild et al. (2018).

The VTLab Speech Production (IRB protocol 2016-1025) task includes the recording of words and sentences that participants produce, which are then analyzed acoustically using TF32 (Milenkovic, 2010) to measure the vowel formants; intelligibility is scored as percent correct (words, consonants, vowels) based on the transcription of lab staff and/or naïve listeners. For each participant, assessment will entail three pre-treatment baseline measures, and post-treatment measures at the completion of the 12-week treatment, and at one, and six months following completion of DS-DxTx. The initial assessment also will include standardized testing using the Hodson Assessment of Phonological Processes-3 to customize treatment plan, Peabody Picture Vocabulary Test, an oral motor exam, Intelligibility in Context Scale (ICS) questionnaire, parent questionnaires, and language samples to measure Mean Length of Utterance, and when sample is adequately length for intelligibility scoring.

Consultation with a statistician, available through Waisman Center core services, will be used.

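### Aim 2 ties unchanged low-vowel accuracy to a craniofacial cause, but percent correct pools /a/–/æ/ confusions with all other low-vowel errors, and the planned F2 difference is not part of that rule

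*Combined protocol and SAP*

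**What the plan says.** Aim 2, in Specific Aims/Study Objectives, asks how far craniofacial dysmorphology accounts for reduced intelligibility and promises both perceptual and acoustic measures.

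- **Perceptual measure.** "Perceptual measure will include percent accurate identification of the low vowels", with /a/ set against /æ/ and labelled as percent vowels correct, compared before and after treatment.
- **No-change rule.** Accuracy on the low vowels "is hypothesized to remain unchanged if reduced accuracy is predominantly due to craniofacial dysmorphologies". Only percent vowels correct appears in this sentence.
- **Effectiveness rule.** "Increased difference of the second resonant frequency (F2) for the low vowels", which the plan links to front/back tongue movement, "combined with improved perceptual identification of the low vowels (percent vowels correct) will implicate the effectiveness of intensive treatment". This rule needs both measures.

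Background and Significance gives the mechanism for these vowels: "the smaller anterior facial skeleton in speakers with DS limited/compressed the tongue's front/back movements to distinctly produce the vowels" /a/ and /æ/.

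Statistical Considerations describes the scoring: "intelligibility is scored as percent correct (words, consonants, vowels) based on the transcription of lab staff and/or naïve listeners". The Measures section lists the same percent-correct scores. Neither section, nor Aim 2, plans a table of what each low vowel was heard as or a split of errors by type.

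**The concern.** The stated mechanism makes /a/ and /æ/ less distinct from each other. The error that bears on it most directly is one of them heard as the other. Percent correct also falls when a low vowel is heard as some unrelated vowel or is left out.

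Such errors are plausible in these boys. Specific Aims/Study Objectives names motor impairment, phonological disorder and hearing loss beside craniofacial causes. The treatment works on these too: the Approach section describes Cycles as covering phonological error patterns in general and as possibly helping with fluctuating hearing and motor planning.

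The treatment could therefore raise low-vowel accuracy through errors unrelated to the front/back contrast. Under the no-change rule, that rise would count against a predominantly craniofacial cause although the contrast named in the mechanism had not moved. At stake is the anatomical inference of Aim 2; Aim 1 is not affected.

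**Working it through.** The plan gives no figure to reproduce: there are no error rates, effect sizes or power calculations for Aim 2. All rates below are assumptions.

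**Identity.** For low-vowel tokens, let P be percent correct, F the percent heard as the other low vowel, and O the percent with any other error. Then P = 100 − F − O, so change in P = −(change in F) − (change in O). The no-change rule looks only at the change in P.

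**Three outcomes from one assumed baseline (P 60, F 20, O 20).**

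| Case | What changes | P after | F after | O after |
|---|---|---|---|---|
| A | other errors fall, confusion fixed | 100 − 20 − 5 = 75 | 20 | 5 |
| B | confusion falls, other errors rise | 100 − 5 − 35 = 60 | 5 | 35 |
| C | confusion falls, other errors fixed | 100 − 5 − 20 = 75 | 5 | 20 |

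A and C give the same gain of 75 − 60 = 15 points, but confusion is unchanged in A and down by three quarters in C. B shows no gain although confusion falls as far as in C.

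**Range for case A.** With baseline error e = 100 − P and a share s of errors being /a/–/æ/ confusions, other errors are e(1 − s). Halving them with F fixed adds e(1 − s)/2 points:

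| Baseline P | s = 25% | s = 50% | s = 75% | s = 100% |
|---|---|---|---|---|
| 50 | 50 × 0.75/2 = 18.75 | 12.5 | 6.25 | 0 |
| 60 | 15 | 10 | 5 | 0 |
| 70 | 11.25 | 7.5 | 3.75 | 0 |
| 80 | 20 × 0.75/2 = 7.5 | 5 | 2.5 | 0 |

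The gain is 0 only when every error is an /a/–/æ/ confusion.

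**Range for case B.** To hide a halving of confusion, other errors must rise by e × s/2. That runs from 20 × 0.25/2 = 2.5 points to 50 × 1/2 = 25 points.

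**Where F2 enters.**

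- In case A, the F2 difference would be expected not to widen, so the effectiveness rule would not be met. The no-change prediction nevertheless fails because P rose. The plan does not say how to read that combination.
- In case B, P matches the craniofacial prediction while F2 would be expected to separate. The two measures would visibly disagree, but the no-change rule does not call on F2.

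**The case against.** The strongest reply is that Aim 2 already has a measure specific to the front/back contrast. The F2 difference is planned, tied to tongue movement, and required together with better identification before treatment is called effective. This stands. A reader might infer that Aim 2 decides between anatomy and trainability on percent correct alone; the documents do not support that for the effectiveness conclusion. It does hold for the no-change sentence, which mentions no acoustic result.

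Other points on that side:

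- **Flat accuracy hiding a real improvement (case B).** This needs other errors to rise by about as much as confusion falls, during treatment focused on these vowels. Nothing in the documents suggests such a rise. It is possible, but the point rests on case A.
- **Replacing percent correct with the confusion rate.** A reader might infer that this is the remedy. The documents do not support it. They say the vowels are produced less distinctly, not what listeners will hear. A compressed /æ/ or /a/ could be heard as an intermediate vowel, which a bare confusion rate would miss. Aim 2 also concerns intelligibility, which percent correct addresses directly, and describes craniofacial effects more broadly than this one confusion.
- **Loss of information.** The plan says its perceptual measure will include percent correct, and transcriptions are made. Error types could be tabulated later; what is missing is a stated intention to do so and to use the result.
- **A two-choice task.** The words setting /a/ against /æ/ could mean that listeners choose between these two vowels only. Then O = 0, P = 100 − F, and the concern disappears. Statistical Considerations describes transcription, which points to open responses, but it refers to a cited study for detail, so the documents do not settle this.

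**Conclusion.** The concern holds in a limited form. The no-change rule rests on a pooled percent correct, while the mechanism it is meant to test concerns the distinction between two vowels. A gain from correcting other errors could therefore appear to refute the anatomical hypothesis with the front/back contrast unchanged. The F2 difference partly protects the effectiveness conclusion but not this inference.

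The size cannot be stated from the documents. Under the assumed ranges above, the shift is 0 to 18.75 points if other errors halve; at 60% accuracy with half of errors being confusions it is 10 points. The conclusion assumes that listeners may report vowels other than the two low ones, and that some low-vowel errors are not /a/–/æ/ confusions.

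This is an inexpensive improvement to how Aim 2 is read. It does not make percent correct the wrong measure.

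**What to change.** Keep percent low vowels correct and the F2 difference, and add the following to Aim 2 and Statistical Considerations.

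1. From the same transcriptions, tabulate for each boy and visit, separately for /a/ and /æ/, the tokens heard as intended, heard as the other low vowel, and heard as another vowel. List which other vowels were heard, so that intermediate ones are visible, and show omitted or unscorable vowels separately.
2. State that the no-change inference will be read from percent correct, the /a/–/æ/ confusion rate and the F2 difference together, and say how disagreement among them will be reported.
3. State the response set of the listener task. If only /a/ or /æ/ can be given, say so; percent correct is then already 100 minus the confusion rate and the table adds nothing.

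**Cost.** Wording and tabulation, with no new recordings or listeners, provided the transcripts keep the vowel heard and not just a right/wrong mark. The drawback is that confusion counts per boy will be smaller than counts of all errors, so the rate will be less precise. The documents do not give the number of low-vowel tokens, so the counts should be shown beside the rates.
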